Study endpoints:	Primary endpoint: 
• Change of best corrected visual acuity in ETDRS letters score at month 12 when compared with baseline (measured by the difference in ETDRS letters score between month 12 and baseline) Secondary endpoints: 
• Number of treatments with ranibizumab up to 6, 12, 18 and 24 months of treatment respectively• Mean average change in BCVA at 6, 12, 18 and 24 months after initial treatment• Macular thickness (as measured with OCT) at 6, 12, 18 and 24 months after initial treatment• Time to reach target HbA1c• Number of neovascular complications: need for panretinal laser photocoagulation (PRP)• Rates of ocular and of systemic AEs (retinal detachment, central retinal artery occlusion, endophthalmitis; rates of stroke, myocardial infarction, severe hypoglycemia)

Medical condition:	Diabetic patients with visual impairment due to diabetic macular edema (DME)								
Principal inclusion criteria:	
 • Patients with diabetic macular edema relevant to visual acuity • OCT central retinal thickness $\geq 250\mu\text{m}$ • HbA1c $> 6,5\%$ at initial visit • BCVA ≤ 0.8 and ≥ 0.05 • Age ≥ 18 years • Written patient informed consent given 								
Principal exclusion criteria:	
 • Previous treatment with intravitreal drugs in last 6 months • Vitreous hemorrhage as a consequence of proliferative retinopathy • Pregnancy • Blood pressure of $\geq 180/100$ (or uncontrolled pressures under pharmacological therapy) • Chronic systemic or ocular inflammatory/autoimmune diseases (e.g. inflammatory bowel disease, Addison's disease, Cushing Syndrome, Uveitis) • Systemic cortisone or anti-VEGF therapy • Acute systemic or ocular infectious diseases 								
Name of investigational medicinal product (IMP):	Ranibizumab (Lucentis®)								
Investigational medicinal product – dosage and method of administration:	Ranibizumab – three initial monthly intravitreal injections (0.05 mg) and subsequent injections until visual acuity reached maximum (maximum of visual acuity defined as stable visual acuity under treatment with ranibizumab on three consecutive monthly control visits)								
IMP or therapy used as a comparator – dosage and method of administration:	not applicable								
Duration of treatment:	12 months treatment period with Ranibizumab Total follow-up is 12 months (with PRN treatment option)								

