4.4. Withdrawal of trial subjects after trial start

Study subjects will be early discontinued from participation in the study if

- they withdraw consent from participating in the study
- no response to the ranibizumab treatment is observed, defined as persisting macular edema without any reduction of central retinal thickness after 3 consecutive monthly injections
- they present visual loss defined as ≥ 30 ETDRS Letters when compared with the baseline
- they develop vitreous bleeding due to active neovascularisation of the retina or optic disc confirmed by fluorescein angiography with need of surgical treatment (vitrectomy)
- any other clinical adverse event (AE), laboratory abnormality, illness or other medical condition or situation occurs that would not go along with the best interest of the patient in case of continuing the participation.

Note: Each patient should be followed-up even if the study treatment is discontinued.

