4.4.1. Procedures for premature withdrawal from treatment during the trial

In case of patient withdrawal during the study period all data collected until this point of time will be stored according to AMG §40, 2a, 3. The patient must not be replaced.

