4.6.1. Treatments to be given

In all patients (in both study arms) the diabetic macular edema will be treated with intravitreally given ranibizumab.

Dosage and administration of Ranibizumab

Injections are administered according to the current summary of product characteristics Lucentis®, i.e. monthly until maximum BCVA can be observed:

Starting at visit 1, ranibizumab will be administered intravitreally in a multiple-dose regimen of 0.5 mg of ranibizumab every month for a total of 3 injections and as a PRN treatment thereafter (subsequent injections until maximum BCVA is observed).

Injection is discontinued when

- no BCVA improvement in spite of treatment is seen after the first three injections (i.e. after three consecutive monthly visits)

BCVA assessments will take place monthly. Monthly injections are resumed when

- decrease in BCVA due to worsening of DME in the opinion of the investigator is observed

Injections are continued until BCVA improvement is seen after three consecutive monthly visits.

If a subject is unable to receive study drug because of medical or personal reasons, treatment should be resumed within 2 weeks of the scheduled treatment. If a subject is unable to receive study drug within 2 weeks of the scheduled treatment, the subject will be allowed to miss the scheduled dose and resume treatment at the next regularly scheduled time. Dosing should not occur more frequently than every 4 weeks. Missed doses will not be replaced.

Ranibizumab Injection

Procedures will be implemented to minimise the risk of potential adverse events associated with serial intraocular injections (e.g., endophthalmitis). Aseptic technique must be observed by clinic staff involved in the injection tray assembly, anesthetic preparation and administration, and study drug preparation and administration. In addition to the procedures outlined in the protocol, added safety measures in adherence to specific institutional policies associated with intraocular injections should be observed.

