4.6.8. Previous and concomitant medication

Permitted concomitant therapies include cataract surgery. Other surgical therapies, e.g. vitrectomy, are not permitted during the study and will be considered treatment failure.

Similarly, other pharmacological treatments for macular edema, e.g. triamcinolone or other steroids or other anti-VEGF drugs (local or systemic) are not permitted during the study period.

Any therapy (except medications which are excluded by the trial's exclusion criteria) is allowed for treatment of the underlying disease diabetes mellitus.

Concomitant therapy will be documented on the appropriate trial database/CRF pages.

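### Section 4.4 ends study participation on three post-randomisation clinical criteria, its closing Note points to continued follow-up, and nothing requires a month-12 BCVA for these patients

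*Combined protocol and SAP*

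**What the plan says.** Section 4.4 opens its list with "Study subjects will be early discontinued from participation in the study if". Three of the five entries are specific clinical criteria:

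- no response to ranibizumab, "defined as persisting macular edema without any reduction of central retinal thickness after 3 consecutive monthly injections";
- a loss of 30 or more ETDRS letters from baseline;
- vitreous bleeding from active neovascularisation that needs vitrectomy.

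The other two are withdrawal of consent and a general best-interest clause. The section ends with a Note: "Each patient should be followed-up even if the study treatment is discontinued".

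Section 4.4.1 is headed "Procedures for premature withdrawal from treatment during the trial" and says: "In case of patient withdrawal during the study period all data collected until this point of time will be stored". Section 4.6.8 states that "other anti-VEGF drugs (local or systemic) are not permitted during the study period". Section 4.6.8.1 allows a patient to be withdrawn from the study for insufficient effect and then to receive any treatment thought necessary.

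The primary endpoint (6.1.3) is the change in BCVA from baseline to month 12, analysed in the ITT population. When month 12 is missing, 6.1.3 takes the nearest measurement in time, before or after, provided that it lies at or beyond 3 months. Section 6.1.4 carries the last BCVA and thickness value forward for the secondary endpoints.

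**The concern.** The opening sentence of 4.4 ends participation. The Note speaks only of stopping study treatment. Site staff can read the section either way, so two similar patients may be handled differently.

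The three criteria are all met after randomisation, and all concern outcomes on which the arms may differ. Thickness is itself a secondary endpoint, and the introduction gives an effect of better metabolic control on macular edema as the question under study. If that effect exists, the proportion meeting the thickness criterion need not be equal in the two arms. An early acuity would then replace the month-12 acuity more often in one arm than in the other, within the primary analysis.

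The ban on other drugs for macular edema adds to the risk. A patient who needs a different drug can obtain it only outside the study period, which makes a real exit plausible.

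**Working it through.** No planned figure is in dispute here. The check compares the texts and follows a withdrawn patient through the analysis rules.

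**1. Which text governs?**

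| Text | Points to | What it leaves open |
|---|---|---|
| 4.4, opening sentence | Leaving the study | – |
| 4.4, Note | Continued follow-up | Tied to treatment stopping; names no visit, assessment or duration |
| 4.4.1, heading | Stopping treatment only | The text beneath covers storage of data already collected |
| 4.2 | Active follow-up to limit attrition | General; discontinued patients not mentioned |
| 4.6.8 and 4.6.8.1 | Leaving the study to receive other treatment | No acuity measurement after exit |
| 4.6.9 | Medical care after withdrawal | Care, not outcome assessment |
| Tables 2 and 3 | Monthly BCVA and OCT to month 24 | Not stated whether they apply after discontinuation |

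The texts do not settle the question, and none says that a discontinued patient still has the month-12 BCVA.

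**2. When can a patient leave?** Table 2 gives fixed injections at visits 1 to 3, so the first visit after the third injection is visit 4. Visit 1 is treatment start, and section 4.7.5 sets 4-week intervals:

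- visit 4: 3 × 28 = 84 days after the first injection, with the ± 1 week window 77 to 91 days;
- visit 12: 11 × 28 = 308 days;
- gap between them: 308 − 84 = 224 days.

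A patient who leaves at visit 4 misses 8 BCVA visits to month 12 (visits 5 to 12) and 12 in the second year, that is 20 of the 24 scheduled after screening. The visual-loss and bleeding criteria have no fixed time.

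**3. What enters the primary analysis?** Table 2 labels visit 1 as month 1, so visit 4 carries the label month 4 and passes the 3-month condition in 6.1.3. If it is the last measurement, it is also the nearest one to month 12. It therefore stands in for a value due about 224 days later.

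**4. How does this reach the arm comparison?** Let p be the proportion of an arm removed and s the mean of (substituted BCVA − the month-12 BCVA that would have been observed) among those removed, with I for intensified and R for regular control. The shift in the estimated difference is

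shift = p_I × s_I − p_R × s_R.

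It is zero if p and s are equal in both arms. With a common s it becomes (p_I − p_R) × s.

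The documents give neither p nor s. The following values are assumptions and serve only to show scale:

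| Difference in p (assumed) | Size of s (assumed) | Size of shift |
|---|---|---|
| 10 percentage points | 3 letters | 0.10 × 3 = 0.3 letters |
| 10 percentage points | 5 letters | 0.10 × 5 = 0.5 letters |
| 20 percentage points | 3 letters | 0.20 × 3 = 0.6 letters |
| 20 percentage points | 5 letters | 0.20 × 5 = 1.0 letters |

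Section 6.2 plans for a difference of 2.0 letters. The direction is open. If fewer patients are removed under intensified control, the shift favours that arm when removed patients would have improved later (s < 0), and works against it when they would have worsened (s > 0).

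**The case against.** The best case for the plan is that follow-up is already intended. If the Note did not cover the clinical criteria listed above it, it would have little to apply to. The heading of 4.4.1 speaks of treatment, 4.2 promises active follow-up, Tables 2 and 3 exempt nobody, and 6.1.3 accepts a value after month 12. This stands as evidence of intent. It rules out the stronger reading that the protocol plans to lose these patients. It does not remove the opening sentence or require the measurement.

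A reader might also infer that 4.4.1 stops data collection at withdrawal. It does not say so: it is a retention statement tied to a legal provision.

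A reader might further infer that these patients would have no primary value, would drop out of the ITT analysis and would use up the dropout allowance. That needs 3 months to mean strict elapsed time, about 91 days, which visit 4 reaches only at the edge of its window. By the same measure visit 12, at 308 days or about 10.1 months (308 / 30.44), would not be month 12. The visit label is the consistent reading, so the problem is substitution of an early value and not its absence.

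It is also fair that both arms receive the same ranibizumab regimen, that OCT and BCVA assessments are masked, and that the thickness criterion requires no reduction at all after only about 12 weeks of the glycaemic intervention. A difference in removal is possible but not shown. Nor is an anatomical exit rule wrong merely because injections are guided by acuity: the two rules serve different purposes. Finally, 6.1 leaves details to a statistical analysis plan, but no analysis rule can recover a measurement that was not taken.

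**Conclusion.** The point holds as a conflict within 4.4 that leaves the month-12 BCVA unsecured for patients who meet the thickness, visual-loss or bleeding criterion. Bias in the primary comparison requires that sites act on the opening sentence and that removal, or the later course of acuity among those removed, differs between the arms. The documents establish neither condition, and the size cannot be computed from them; the 0.3 to 1.0 letters shown above rest wholly on assumed inputs. The per-protocol analysis is only a partial check: it requires an endpoint after 6 months, so it leaves out patients who exit at visit 4. The sample size calculation is not called into question. This is an inexpensive improvement that the sponsor should make, not a defect that invalidates the design.

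**What to change.** Reword 4.4 so that the thickness, visual-loss and vitreous-bleeding criteria stop ranibizumab study treatment only. Participation should end only on withdrawal of consent or on a documented decision that continuing is not in the patient's best interest. State that BCVA and OCT continue at the scheduled visits after study treatment stops, at least at months 12 and 24, and that the observed month-12 BCVA is used in the ITT analysis. Align 4.6.8 and 4.6.8.1 so that other treatment for macular edema is allowed, and recorded, once study treatment has stopped.

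The cost is a protocol amendment under section 9, signed by all authors and, where required, approved by the ethics committee and the federal authority. No visits are added, because monthly BCVA and OCT to month 24 are already scheduled. The downside is that some month-12 values will be measured after other treatment. The ITT comparison then includes the effect of that treatment, and the report should say how many patients in each arm received it.

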4.4.1. Procedures for premature withdrawal from treatment during the trial

In case of patient withdrawal during the study period all data collected until this point of time will be stored according to AMG §40, 2a, 3. The patient must not be replaced.

4.5. Closure of trial sites/Premature termination of the clinical trial

4.5.1. Closure of trial sites

Not applicable, this is a monocentric trial.

4.5.2. Premature termination of trial

The sponsor has the right to terminate the trial prematurely if there are any relevant medical or ethical concerns or if completing the trial is no longer practicable. If such action is taken, the reasons for terminating the trial must be documented in detail. All trial subjects still under treatment at the time of termination must undergo a final examination which must be documented. The PCI must be informed without delay if any investigator has ethical concerns about continuation of the trial.

The trial must be terminated if:

- The risk-benefit balance for the trial subject changes markedly
- It is no longer ethical to continue treatment with the IMP
- The sponsor considers that the trial must be discontinued for safety reasons
- It is no longer practicable to complete the trial, e.g. due to scientific reasons

PCI decides on whether to discontinue the trial based on medical data and/or in consultation with the statistician.

4.6. Treatment

Patients are treated with ranibizumab for their underlying disease diabetic macular edema according to the current summary of product characteristics Lucentis®. Treatment will take place at trial site.

4.6.1. Treatments to be given

In all patients (in both study arms) the diabetic macular edema will be treated with intravitreally given ranibizumab.

Dosage and administration of Ranibizumab

Injections are administered according to the current summary of product characteristics Lucentis®, i.e. monthly until maximum BCVA can be observed:

Starting at visit 1, ranibizumab will be administered intravitreally in a multiple-dose regimen of 0.5 mg of ranibizumab every month for a total of 3 injections and as a PRN treatment thereafter (subsequent injections until maximum BCVA is observed).

Injection is discontinued when

- no BCVA improvement in spite of treatment is seen after the first three injections (i.e. after three consecutive monthly visits)

BCVA assessments will take place monthly. Monthly injections are resumed when

- decrease in BCVA due to worsening of DME in the opinion of the investigator is observed

Injections are continued until BCVA improvement is seen after three consecutive monthly visits.

If a subject is unable to receive study drug because of medical or personal reasons, treatment should be resumed within 2 weeks of the scheduled treatment. If a subject is unable to receive study drug within 2 weeks of the scheduled treatment, the subject will be allowed to miss the scheduled dose and resume treatment at the next regularly scheduled time. Dosing should not occur more frequently than every 4 weeks. Missed doses will not be replaced.

Ranibizumab Injection

Procedures will be implemented to minimise the risk of potential adverse events associated with serial intraocular injections (e.g., endophthalmitis). Aseptic technique must be observed by clinic staff involved in the injection tray assembly, anesthetic preparation and administration, and study drug preparation and administration. In addition to the procedures outlined in the protocol, added safety measures in adherence to specific institutional policies associated with intraocular injections should be observed.

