4.7.1.2. Secondary target variables

- Number of treatments with Ranibizumab up to 6, 12, 18 and 24 months of treatment respectively
- Mean average change in BCVA at 6, 12, 18 and 24 months after initial treatment
- Macular thickness (as measured with OCT) at 6, 12, 18, and 24 months after initial treatment
- Time to reach target HbA1c
- Number of neovascular complications: need for panretinal laser photocoagulation (PRP)
- Rates of ocular and of systemic AEs (retinal detachment, Central retinal artery occlusion, endophthalmitis; and rates of stroke, myocardial infarction, severe hypoglycemia)

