4.7.4.1. Description of visits

Screening assessments should be performed 1 to 7 days before treatment start (Visit 1).

Table 2: Investigations during the clinical trial (until month 12)

Visits	Screenig	1	2	3	4	5	6	7	8	9	10	11	12
Month	-1 to -7 days	1	2	3	4	5	6	7	8	9	10	11	12
Procedure	a time frame of ± 1 week is allowed until visit 12												
Inclusion/exclusion criteria	x												
Demographic data & med. history	x												
Informed consent ¹	x												
Pregnancy status ²	x												
Randomization	x												
Study treatment		x	x	x	x ⁵	x ⁵	x ⁵	x ⁵	x ⁵	x ⁵	x ⁵	x ⁵	x ⁵
Clinical lab tests ³	x			x			x			x			x
Blood glucose and blood pressure measurement (group 1) (regular diabetic control) ⁴	x			x			x			x			x
Blood glucose and blood pressure measurement (group 2) (intensive diabetic control)	x	x	x	x	x	x	x	x	x	x	x	x	x
Funduscopy	x			x	x	x	x	x	x	x	x	x	x
BCVA (ETDRS)	x	x	x	x	x	x	x	x	x	x	x	x	x
Slitlamp	x	x	x	x	x	x	x	x	x	x	x	x	x
Fluorescein angiography	x						x						x
Fundus photography	x			x			x			x			x
OCT	x	x	x	x	x	x	x	x	x	x	x	x	x
Concomitant medication	x	x	x	x	x	x	x	x	x	x	x	x	x
AE/SAE (documentation & report)		x	x	x	x	x	x	x	x	x	x	x	x
SCR = Screening, to be performed within one week before study treatment start ¹ written informed consent has to be obtained before any study related investigations are performed ² for women of child-bearing potential a test will be performed at screening; all other women will be asked for pregnancy status. In the course of the trial women of child-bearing potential will be asked for pregnancy status before Ranibizumab treatment or fluorescein angiography ³ triglycerides, HbA1c ⁴ group 1 patients will be cared for diabetes by their general practitioner and will visit the site additionally every three months as indicated ⁵ checkup visit according to local practice & possible PRN therapy													

Table 3: Investigations during the clinical trial (months 12-24: follow-up time)

Visits/Months	13	14	15	16	17	18	19	20	21	22	23	24
Procedure	a time frame of ± 4 weeks is allowed until visit 24											
Ranibizumab treatment ¹	according to local practice & possible PRN therapy											
Clinical lab tests			X			X			X			X
Blood glucose and blood pressure measurement (group 1) (regular diabetic control)			X			X			X			X
Blood glucose and blood pressure measurement (group 2) (intensive diabetic control)			X			X			X			X
Funduscopy			X			X			X			X
BCVA (ETDRS)	X	X	X	X	X	X	X	X	X	X	X	X
Slitlamp	X	X	X	X	X	X	X	X	X	X	X	X

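### As worded, section 4.6.1 ends resumed ranibizumab injections on improvement, against the protocol's own rule of treating until acuity is at its maximum

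*Combined protocol and SAP*

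**What the plan says.** Section 4.6.1 (Treatments to be given) ties dosing to the product label and paraphrases it as "monthly until maximum BCVA can be observed". After three monthly injections of 0.5 mg, treatment is as needed: "subsequent injections until maximum BCVA is observed". Three operational statements follow, in this order:

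- Stop when "no BCVA improvement in spite of treatment is seen after the first three injections".
- Resume monthly injections on a "decrease in BCVA due to worsening of DME in the opinion of the investigator is observed".
- Then: "Injections are continued until BCVA improvement is seen after three consecutive monthly visits".

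The synopsis gives the only definition of maximum acuity: "stable visual acuity under treatment with ranibizumab on three consecutive monthly control visits". It also gives the dose as 0.05 mg. Sections 4.6.5 and 4.6.6 give no dose of their own and refer to 4.6.1. In Table 2 (section 4.7.4.1), the footnote for visits 4 to 12 says only "checkup visit according to local practice & possible PRN therapy".

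Section 4.7.1.2 lists as a secondary variable "Number of treatments with Ranibizumab up to 6, 12, 18 and 24 months of treatment respectively". Section 6.1.4 compares it between arms by ANOVA without covariates at each of the four time points.

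**The concern.** A treat-to-maximum rule stops when acuity has levelled off. The last of the three statements stops when acuity has risen. Followed to the letter, it would take a patient who is still gaining off treatment and keep injecting one whose acuity has settled.

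What is at stake is the meaning of the injection count. Section 2.1 states the hypothesis that intensive diabetes treatment will improve acuity and also lower the need for repeat treatment. The count measures need only if the rule that generates it follows need. For a patient who resumes, a stop on improvement breaks that link.

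**Working it through.** This is mainly a comparison of texts. There is no plan figure to reproduce for the stop rule.

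**1. Direction of each statement**

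| Place | What ends injections |
|---|---|
| 4.6.1, general rule and as-needed clause | maximum acuity |
| Synopsis, definition of maximum | stable acuity, three consecutive monthly visits |
| 4.6.1, stop bullet | no improvement after the first three injections |
| 4.6.1, sentence after the resumption trigger | improvement, three consecutive monthly visits |

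The first three point the same way. The fourth points the other way.

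**2. Can another reading reconcile the fourth?**

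- *Improvement sustained over three visits:* the trigger is still gain, not stability.
- *Lost acuity regained, and seen over three visits:* this is natural after a decline, but it too makes gain the trigger and does not require a plateau.
- *A rule for all injections, since the sentence does not name resumed ones:* it then conflicts directly with the stop bullet just above it.
- *A dropped 'no further':* this restores agreement with the other three and is the likeliest intention, but the reader has to supply the words.

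**3. Direction of the effect on one patient's count (illustration only)**

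Assumptions: monthly visits to month 12 (Table 2); injections at visits 1 to 3, a pause at visit 4, and resumption at visit r, at the earliest r = 5. Acuity is read before the injection. The three visits are r+1, r+2 and r+3, with no injection at the stop visit. A course that stops after three visits has 3 injections (at r, r+1 and r+2); one that never stops has 13 − r by month 12.

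| Course after resumption, r = 5 | Literal sentence | Stable-acuity rule | Difference |
|---|---|---|---|
| Flat acuity | 13 − 5 = 8 | 3 | +5 |
| Gain at every visit | 3 | 13 − 5 = 8 | −5 |

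For r between 5 and 10 the absolute difference is (13 − r) − 3 = 10 − r. That is 2 at r = 8 and 0 at r = 10, and it stays 0 for later resumption. Counting conventions matter too. At r = 5 the difference is 8 − 2 = 6 if the resumption visit counts as the first of the three, and 8 − 4 = 4 if an injection is also given at the stop visit.

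The error can therefore push a count either way. These are extreme courses, so the figures are neither an estimate of the effect nor a bound on it.

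**4. Sample size**

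Section 6.2 uses a difference of 2.0 letters, an SD of 3.5, two-sided alpha of 5% and 85% power. A two-sample t-test calculation gives 55.97, so 56 per arm and 112 in total, as stated. No input depends on the injection rule.

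**5. Dose**

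Synopsis 0.05 mg, section 4.6.1 0.5 mg: 0.5 / 0.05 = 10, a tenfold discrepancy. Sections 4.6.5 and 4.6.6 defer to 4.6.1, so 0.5 mg governs.

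**The case against.** The strongest reply is that the protocol already contains a proper stop rule. The as-needed clause in 4.6.1 covers every injection after the third, resumed ones included, and the synopsis defines its end point. Sections 4.6 and 4.6.1 also bind treatment to the product label. This stands in part: it would be wrong to infer that resumed treatment has no other stop rule. But the general rule and the specific sentence disagree, and a treater looking for what to do after resumption will find the specific one. The label is not among the documents, so it cannot be used to settle the matter, and the protocol's own paraphrase of it is the rule that the sentence contradicts.

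Second, the counts in the illustration need an unusual patient: one who pauses at visit 4, declines within a month, then gains at every visit or stays flat to month 12. Section 4.4 would withdraw a patient with no reduction in retinal thickness after three injections, and section 4.6.8.1 allows withdrawal for insufficient effect. Either could shorten the flat course, and neither is modelled. This stands, and it is why no size is claimed. The section 4.4 criterion rests on thickness, however, so it does not remove an eye with flat acuity and some thinning.

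Third, both arms follow the same text at one site in an exploratory trial. This stands as well. Because treatment is not blinded, a reader might infer that treaters would apply an unclear rule differently by arm, or that month-12 acuity would be biased. The documents show neither.

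Fourth, a reader might infer from the synopsis that patients could receive a tenth of the intended dose. Nothing in the documents supports that; it is a synopsis error that 4.6.1 settles.

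**Conclusion.** The point holds as an internal contradiction in an operative dosing rule. The sentence on continuing injections after resumption makes improvement the stop. The general rule in the same section and the synopsis definition make stable acuity the stop. It is probably a slip, and many treaters may read it as intended. It still deserves correction, because it is the only sentence aimed specifically at continuation after resumption and it feeds a tested secondary endpoint.

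The size of any effect on injection counts is unknown: the documents give neither the number of patients who resume nor the reading that treaters would adopt. No between-arm bias is shown, nor any effect on the primary analysis, sample size or power. The conclusion assumes that the sentence refers to resumed injections, which its placement suggests but its words do not say. If it is a general rule, the contradiction is more direct.

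**What to change.** Replace the one sentence in 4.6.1 with wording such as: *Resumed injections are continued monthly until no further BCVA improvement is seen, i.e. BCVA is stable on three consecutive monthly visits under treatment (maximum BCVA as defined in the synopsis).*

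Leave the stop rule for the first three injections unchanged. Merging initial and resumed courses into one rule looks tidy, but it could require further injections in patients whom 4.6.1 now stops after three, which would change the regimen.

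As a minor correction, change the synopsis dose from 0.05 mg to 0.5 mg.

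The cost is an amendment of a few lines under section 9, submitted to the ethics committee and the federal authority if it is of a kind that needs approval. It requires no additional patients, visits or data.
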